7.2.2 Safety

Toxicity is assessed according to the NCI- CTCAE V4.03 scale during physical examination Identified risks as well as potential risks associated with atezolizumab are extensively described in the Investigator Brochure.

Toxicity is the adverse events graded with the NCI-CTC-AE v4.03 scale, at least possibly related to the treatment.

8 DETERMINATION OF SAMPLE SIZE AND STATISTICAL ANALYSIS

8.1 Sample size

One-year progression-free survival will be estimated in CRC (cohort 1, *closed to inclusions*), in NSCLC (cohort 2, *closed to inclusions*), in RCC (cohort 3, *closed to inclusions*) and in sarcoma (cohort 4, *closed to inclusions*). Within each cohort, a Fleming 1-stage design will be applied to demonstrate that the progression free survival rate at one year is not inferior to 15% but could reach 32%.

To ensure a global alpha risk (Type I error) will be fixed at 0.1 (unilateral), the Bonferroni correction will applied: Out of the 4 cohort, one (RCC cohort) has been closed for lack of accrual and no test will be carried out in this cohort. Therefore, the alpha risk for each test will be 0.033.

To test in each cohort, the hypothesis that the PFS rate is greater than p0 with alpha=0.033 and with a 90% power to detect activity greater than p1, we need to enroll 54 evaluable patients.

If 13 patients or more are alive and free of progression at one year in the cohort, the combined SABR+ atezolizumab will be considered as a success for the corresponding histology.

To take into account a possible rate of 10% of non evaluable patients, and considering that the renal cohort will close after the enrolment of 7 patients, the total number of patients will be 187 = 3 * 60 + 7 to achieve 162 evaluable patients total in the 3 opened cohorts.

In lung cancer and sarcoma patients receiving a second SABR course:

A group of NSCLC and sarcoma patients progressing after their initial treatment with SABR+atezolizumab will be enrolled for a second SABR course. Assuming that up to 50% of patients may display a oligoprogression (i.e. being eligible for a second SABR course), after immune checkpoint blockers, between 25 and 30 patients per cohort are expected to receive a second SABR course. These cohorts size will enable to detect a response rate at 6 weeks of p1=30% versus a response rate below p0=10% at the 10% type I error level (one-sided) and with a 90% power. In each cohort, if 5 or more responses are observed, the second SABR course will be considered as promising. This threshold will be recomputed based on the actual number of patients re-irradiated in each cohort.

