		ed as the proportion of patients who cannot receive the relative atezolizumab dose intensity below 75% of the slow 900 mg).									
Sample size	This is an open-label non-co	omparative phase II trial with four cohorts of patients.									
determination	One-year progression-free survival rate will be estimated in CRC (cohort 1), in NSCLC (cohort 2) and in RCC (cohort 3) and in sarcoma (cohort 4). In each cohort a Fleming 1-stage design will be applied to demonstrate that the progression free survival rate at one year is not inferior to 15% but could reach 32%.										
	To ensure a global alpha risk (Type I error) will be fixed at 0.1, one-sided the Bonferroni correction will applied; Cohort 3 is stopped for lack of accrual and no test will be performed. Three tests will be carried out and the alpha risk for each test will be 0.033.										
		hypothesis that the PFS rate is greater than p0 with % power to detect activity greater than p1, we need to									
		alive and free of progression at one year in the cohort, ezolizumab will be considered as a success for the									
	To account for possibly 10% of non evaluable patients, 60 patients will be enper cohort (RCC excluded). Considering that the RCC cohort will be closed a patients, the overall expected sample size will then be 187 evaluable patient patients with NSCLC, 7 with RCC, and 60 with CRC and 60 with sarcoma).										
	SABR + atezolizumab will be atezolizumab. Assuming the being eligible for a second checkpoint blockers, betwee receive a second SABR response rate at 6 weeks of	and sarcoma progressing after their initial treatment with the enrolled for a second SABR course while continuing at up to 50% of patients may have oligoprogression (i.e. and SABR course) after the investigational immune there 25 and 30 patients per cohort are expected to course. These cohorts size will enable to detect a f p1=30% versus a response rate below p0=10% at the sided) and with a 90% power.									
Number of patients	Total: 138	France and Spain									
Duration of the	Inclusion	3 years									
trial	Treatment	Until disease progression or unacceptable toxicity									
		(estimation: 2 years)									
		In patients who have not progressed after 2 years of treatment, it is appropriate to consider and discuss treatment discontinuation, which will be proposed if active disease is not detected on PET scan.									
	Follow-up	Until disease progression or up to maximum 1 year									

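### The success rule of 13 or more out of 54 has an exact one-sided type I error of 5.3%, not 3.3%, and no cut-off at 54 patients gives both the stated alpha and 90% power

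*Protocol*

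**What the plan says.** Protocol section 8.1 fixes every input to the primary decision rule.

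- **Design:** "Within each cohort, a Fleming 1-stage design will be applied", with the null and alternative given as "progression free survival rate at one year is not inferior to 15% but could reach 32" per cent.
- **Overall error:** "To ensure a global alpha risk (Type I error) will be fixed at 0.1 (unilateral"). The renal cohort is closed and not tested, so the split is over three cohorts: "Therefore, the alpha risk for each test will be 0.033". The synopsis agrees: "Three tests will be carried out and the alpha risk for each test will be 0.033".
- **Size:** "with alpha=0.033 and with a 90% power to detect activity greater than p1, we need to enroll 54 evaluable patients".
- **Rule:** "If 13 patients or more are alive and free of progression at one year in the cohort", the combination counts as a success for that histology.

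Allowing for 10% non-evaluable patients, 60 are enrolled in each tested cohort. Neither section 8.1 nor the synopsis describes the 0.033 as approximate. For the secondary question on the second SABR course, section 8.1 says that the threshold will be recomputed for the number of patients actually re-irradiated. It makes no such provision for the primary cut-off of 13.

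**The concern.** The primary rule is a count out of 54, so its error rates are exact binomial tail probabilities and can be checked directly. Under the null only 54 × 0.15 = 8.1 successes are expected. With a count that small, the distribution is skewed and moves in coarse steps, and a normal approximation without continuity correction can misstate the upper tail.

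This rule alone decides whether the combination is declared a success in colorectal cancer, lung cancer and sarcoma. If its true alpha exceeds 0.033, the Bonferroni split, which is the plan's only control of multiplicity, does not hold the global 10%. The error also runs in the anti-conservative direction.

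**Working it through.** **Inputs (all from section 8.1).** p0 = 0.15, p1 = 0.32, n = 54, cut-off r = 13, alpha per test 0.10/3 = 0.0333 (stated as 0.033), power 0.90.

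**Step 1: reproduce the plan's figures.** The one-sample normal approximation is

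n = [(z₁₋α √(p0 q0) + z₀.₉₀ √(p1 q1)) / (p1 − p0)]²

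With √(0.15 × 0.85) = 0.357 and √(0.32 × 0.68) = 0.466, this gives n = 54.3 (alpha 0.1/3) or 54.4 (alpha 0.033), which matches 54. The critical count is n p0 + z₁₋α √(n p0 q0) = 8.1 + 1.834 × 2.624 = 12.91, which rounds up to 13. The approximation credits 13 or more with alpha = 1 − Φ((13 − 8.1)/2.624) = 0.031 and power 0.894. This is where 54 and 13 come from.

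**Step 2: exact operating characteristics at n = 54.** Alpha = P(X ≥ r | n, p0) and power = P(X ≥ r | n, p1), with X binomial:

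| Cut-off | Exact alpha | Exact power |
|---|---|---|
| ≥ 12 | 0.1014 | 0.9580 |
| ≥ 13 (plan) | 0.0531 | 0.9215 |
| ≥ 14 | 0.0256 | 0.8660 |
| ≥ 15 | 0.0113 | 0.7895 |

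No row has alpha at or below 0.033 together with power of at least 0.90. Even with a continuity correction, the normal approximation gives 0.0468 for 13 or more.

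**Step 3: smallest size that meets both targets.** An exact search gives n = 60 evaluable with 15 or more successes (alpha 0.0291, power 0.9057). At 10% non-evaluable that is 60/0.9, or 67 enrolled.

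**Step 4: family-wise error over three cohorts, all null.**

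- Cut-off 13: 1 − (1 − 0.0531)³ = 0.151 if the cohorts are independent; upper bound 3 × 0.0531 = 0.159.
- Cut-off 14: 0.075 if independent; upper bound 0.077.

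**Step 5: what a borderline success would show.** At 13/54 (24.1%), the exact one-sided lower confidence limit at the plan's own 0.033 level is 14.0%, below the null of 15%. The plan would call this a success although it does not reject its own null at its own level.

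**Step 6: sensitivity to the number evaluable.** If all 60 enrolled patients in a cohort were evaluable and 13 were kept, exact alpha would be 0.106 in that cohort, more than the whole trial's budget. The smallest cut-off with exact alpha ≤ 0.033 varies with n:

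| Evaluable n | Cut-off | Exact alpha | Exact power |
|---|---|---|---|
| 54 | 14 | 0.0256 | 0.866 |
| 55 | 14 | 0.0297 | 0.884 |
| 56 | 15 | 0.0159 | 0.836 |
| 57 | 15 | 0.0187 | 0.857 |
| 58 | 15 | 0.0218 | 0.875 |
| 59 | 15 | 0.0252 | 0.891 |
| 60 | 15 | 0.0291 | 0.906 |

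**The case against.** The best defence is that the sponsor applied a recognised method consistently. The normal approximation yields both 54 and 13, so nothing was miscalculated within that method. This stands as an account of where the figures came from. It does not make the stated alpha true: the rule is a count with a known distribution, and the protocol does not present 0.033 as approximate. Its secondary rule of 5 or more responses after a second SABR course does meet its stated 10% and 90% exactly at 25 patients (0.098 and 0.910).

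A second argument is that 5.3% per cohort is tolerable in a non-comparative phase II trial, and that the 15.1% arises only if all three cohorts are null. Both statements are fair. But the protocol itself chose a 10% global limit and a Bonferroni split to secure it, and the all-null case is one that the split is meant to cover.

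A third point is that a two-sided 95% interval is a poor yardstick here. For 13/54 it runs from 13.5% to 37.6% and includes 15%, but the intervals for 14/54 and 15/60 also include 15%, because such an interval corresponds to a one-sided 2.5% test. That is correct, so the argument rests instead on the one-sided limit at 0.033 in Step 5.

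Finally, all cohorts are closed and the trial is open-label, so changing a success threshold now needs care. This bears on timing and documentation, not on whether the stated error rate is wrong.

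**Conclusion.** The concern holds. The rule of 13 or more out of 54 has an exact one-sided type I error of 5.3% against the stated 3.3%, a ratio of 0.0531/0.033 = 1.6. The global error is 15.1% with independent cohorts and at most 15.9%, against the stated 10%. The stated combination of 54 patients, alpha 0.033 and 90% power cannot be achieved with any cut-off; the valid cut-off of 14 has 86.6% power.

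The per-cohort result needs no assumption beyond the plan's own inputs and a binomial count among 54 evaluable patients. The 15.1% further assumes that all three cohorts are null and independent; the 15.9% bound does not need independence. Because this is the primary decision rule and the error is anti-conservative, it should be corrected before the primary analysis.

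**What to change.** In section 8.1, and wherever the synopsis repeats the rule, state that the cut-off comes from the exact binomial distribution and replace 13 by 14 or more of 54, with exact alpha 0.026 and power 87%. If all 60 patients in a cohort are evaluable, use 15 or more of 60 (alpha 0.029, power 90.6%).

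For any other evaluable number, define the cut-off as the smallest count with exact one-sided alpha no greater than 0.033, as in the Step 6 table, and report the resulting power. The value 14 must not be carried upward: from 56 evaluable patients its alpha exceeds 0.033 (0.0343 at 56). This parallels the recomputation that section 8.1 already provides for the second SABR course.

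Fix the rule in a dated amendment before the one-year outcome counts are examined. If the sponsor prefers to keep 13 of 54, the protocol should instead state an exact alpha of 5.3% per cohort and about 15% to 16% overall, and withdraw the claim of a 10% global error.

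The cost is wording only, with no new patients. The price is candour about power: 86.6% rather than 90% at 54 evaluable patients, and between 83.6% and 90.6% across 54 to 60.

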4.3 Withdrawal criteria from study treatment and/or from the study

Premature discontinuation of study treatments does not mean that the patient prematurely stops the participation in the study.

The reasons for premature discontinuation of study treatements are:

- No clinical benefit, in the opinion of the investigator, for continuing with the study drug administration
- Progressive disease according to RECIST v1.1 criteria*
- Unacceptable toxicity or symptomatic deterioration attributed to disease progression after an integrated assessment of radiographic data, biopsy results (if available) and clinical status
- Adverse events which preclude further study drug administration as described in section 5.3.1 and 5.3.2
- Pregnancy or intent to become pregnant
- Major deviation to protocol if it interferes with the study evaluations and/or if it jeopardises patient's safety, e.g. any medical event requiring administration of an unauthorised concomitant treatment
- Patient's removal
- Stopping rule, as defined in section 8.2, are fulfilled
- Study terminated by the sponsor
- * However, if following conditions are met, patients will be permitted to continue atezolizumab treatment:
 - Evidence of clinical benefit as assessed by the Investigator,
 - Absence of symptoms and signs (including worsening of laboratory values, e.g., new or worsening hypercalcemia) indicating unequivocal progression of disease,
 - No decline in ECOG performance status that can be attributed to disease progression, and
 - Absence of tumour progression at critical anatomical sites (e.g., leptomeningeal disease) that cannot be managed by protocol-allowed medical interventions.

The reasons for premature discontinuation of the study drug and entire study are:

- Consent withdrawal
- Death
- Completed study follow-up

Patients who discontinue the study drug will have follow-up procedures performed as shown in Table 1 and in section 6.3.

If a patient does not return for a scheduled visit, every effort should be made to contact him (her). In any circumstance, every effort should be made to document the patient outcome. The investigator should inquire about the reason for withdrawal, requests the patient to return for a final visit, and follow-up with the patient regarding any unresolved adverse events. The early termination final visit should include all assessments listed for the follow-up visit.

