7 EVALUATION CRITERIA

7.1 Primary criterion

In each cohort, progression-free survival rate at one year is defined as the rate of patients alive and free of progression at one year from treatment initiation. Progression is defined using RECIST 1.1. criteria, or death, whatever the cause of death, whichever occurs first.

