8.3 Data Analysis

8.3.1 General Considerations

- Statistical analysis for this study will be the responsibility of the Sponsor. For continuous variables, summary statistics will include number of patients, mean, standard deviation, median, interquartile range, minimum, and maximum. Categorical endpoints will be summarized using number of patients and frequency in %. Missing data will not be imputed.
- The interpretation of the study results will be the responsibility of the investigators, pharmacokineticist and statistician.
- Exploratory analyses of the data not described below will be conducted as deemed appropriate.

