Patients with a global deterioration of health status requiring discontinuation of treatment without objective evidence of disease progression at that time should be reported as "symptomatic deterioration". Every effort should be made to document the objective progression even after discontinuation of treatment.

Table 1.3. Evaluation of overall best response

Target lesions	Non-target lesions	New lesions	Overall response
CR	CR	No	CR
CR	Non-CR / Non- PD	No	PR
CR	Not evaluated	No	PR
PR	Non-PD or not all	No	PR

	evaluated		
SD	Non-PD or not all evaluated	No	SD
Not all evaluated	Non-PD	No	Not evaluated
PD	Any	Yes or No	PD
Any	PD	Yes or No	PD
Any	Any	Yes	PD

When SD is believed to be the best response, follow-up measurements must have met the SD criteria at least once after study entry at a minimum interval of six (6) weeks.

21 APPENDIX 5: mRECIST CRITERIA MODIFIED RESPONSE EVALUATION CRITERIA IN SOLID TUMORS

Conventional response criteria may not be adequate to characterize the anti-tumor activity of immunotherapeutic agents like Atezolizumab, which can produce delayed responses that may be preceded by initial apparent radiological progression, including the appearance of new lesions. Therefore, modified response criteria have been developed that account for the possible appearance of new lesions and allow radiological progression to be confirmed at a subsequent assessment. In this protocol, patients will be permitted to continue study treatment even after modified Response Evaluation Criteria in Solid Tumors (RECIST) criteria for progressive disease are met if the risk/benefit ratio is judged to be favorable.

Modified RECIST is derived from RECIST, Version 1.1 conventions ¹ and immune-related response criteria ² (irRC). When not otherwise specified, RECIST v1.1 conventions will apply.

Modified RECIST and RECIST, Version 1.1: Summary of Changes

	RECIST v1.1	Modified RECIST
New lesions after baseline	Define progression.	New measurable lesions are added into the total tumor burden and followed.
Non-target lesions	May contribute to the designation of overall progression	
Radiographic progression	First instance of □ 20% increase in the sum of diameters or unequivocal progression in non-target disease	Determined only on the basis of measurable disease; must be confirmed by a consecutive assessment 4 weeks from the date first documented

DEFINITIONS OF MEASURABLE/NON-MEASURABLE LESIONS

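### The primary success bar rests on an undefined evaluable group, with no rule for treated patients whose one-year status is unknown; depending on who is counted, the false-success risk per cohort can reach about 10.5% against the stated 3.3%

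*Protocol*

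**What the plan says.** Section 7.1 gives the primary endpoint as a proportion: "progression-free survival rate at one year is defined as the rate of patients alive and free of progression at one year from treatment initiation". Death from any cause counts as an event. Section 8.1 applies a single-stage Fleming design in each cohort to show that "the progression free survival rate at one year is not inferior to 15% but could reach 32" per cent. With three tests sharing a one-sided 10%, "the alpha risk for each test will be 0.033". The section asks for 54 evaluable patients with 90% power and declares success at 13 or more in the cohort. It raises enrolment to 60 "To take into account a possible rate of 10% of non evaluable patients".

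Evaluable is not defined and no efficacy population is named; Section 8.3.3 defines a population for safety only. The Synopsis applies the word to all 187 patients, whereas Section 8.1 treats 187 as the number enrolled and 162 as evaluable. Section 8.3.1 states "Missing data will not be imputed".

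The protocol also foresees failure without a RECIST event. Section 4.3 lists, separately from RECIST progression, "No clinical benefit, in the opinion of the investigator, for continuing with the study drug administration". Appendix 4 says that patients who stop because of general deterioration "without objective evidence of disease progression at that time should be reported as" symptomatic deterioration. Under Section 6.3, patients who stop for disease progression have one end-of-study visit, and no imaging is listed for it.

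**The concern.** The bar of 13 was derived for one denominator, but the protocol does not fix who belongs in it. A patient who stops for lack of benefit or symptomatic decline, and has no later scan, may have no RECIST status at one year. If such patients leave the denominator and fail more often than the rest of the cohort, the remaining group looks better than the treated population. The trial is single-arm and tested against a fixed 15%, so no control group shares the loss and any enrichment raises the chance of a false success.

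There is also a gap in the other direction. Section 8.1 recomputes the threshold for the second SABR course from the actual number re-irradiated, but says nothing similar for the primary bar. If more than 54 patients prove evaluable, a bar of 13 becomes easier to reach by chance.

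**Working it through.** **Inputs** (Section 8.1): p0 = 0.15, p1 = 0.32, one-sided alpha 0.033 per cohort, power 0.90, 54 evaluable, 60 enrolled, bar 13.

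**1. The plan's own figures.**
- Normal approximation: n = [(z(0.967)·√(0.15·0.85) + z(0.90)·√(0.32·0.68)) / 0.17]² = 54.4, against 54 stated.
- Cut-off: 54·0.15 + 1.838·√(54·0.15·0.85) = 8.1 + 1.838·2.624 = 12.92, so 13.
- Inflation: 54 / 0.90 = 60.

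The design reproduces.

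**2. Exact error rates of the rule, nobody missing.** With X ~ Binomial(n, p):

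| Rule | Alpha at 15% | Power at 32% |
|---|---|---|
| 13 of 54 | 0.053 | 0.921 |
| 14 of 54 | 0.026 | 0.866 |

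The bar of 13 therefore exceeds 0.033 before any question of missing status. This is a separate defect. The effect of exclusion has to be measured from 0.053 (or from 0.026 if the bar is corrected to 14), not from 0.033.

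**3. Worst case: 60 treated, true rate 15%, six left out, all failures.** Expected successes are 60·0.15 = 9, so the rate among the 54 is 9/54 = 16.7%, a shift of 1.7 points.
- Treating the 54 as Binomial(54, 0.167): P(≥13) = 0.104, P(≥14) = 0.056.
- Treating the successes as Binomial(60, 0.15), since dropping failures removes none: P(≥13) = 0.106, P(≥14) = 0.058.

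That is about 10.5% against 5.3%, or about 5.7% against 2.6%.

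**4. Intermediate case: three of the six are certain failures, three are like the rest.** Rate among the 54 = (9 − 3·0.15)/54 = 0.158; P(≥13) = 0.076, P(≥14) = 0.039.

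**5. When the bias vanishes.** At a true rate of 15%, random exclusion already removes failures 85% of the time. If five of the six are failures and one a success, the rate is (9 − 1)/54 = 14.8% and P(≥13) = 0.049, practically no bias. Upward bias needs a failure share among the excluded above about 85%.

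**6. All 60 counted, bar left at 13.** P(X ≥ 13) for Binomial(60, 0.15) = 0.106.

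**7. All 60 counted, with its own bar.**

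| Bar of 60 | Alpha at 15% | Power at 32% |
|---|---|---|
| 14 | 0.058 | 0.946 |
| 15 | 0.029 | 0.906 |

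The smallest bar within 0.033 is 15. If 32% holds only among patients with known status and losses are uninformative, the all-treated rate is 0.32·0.95 = 0.304 with 5% lost (power 0.854) and 0.32·0.90 = 0.288 with 10% lost (power 0.784).

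**The case against.** A reader might infer that the protocol itself removes clinical failures from the test. It does not say so. The 10% appears only as an enrolment allowance, and non-evaluable could equally mean ineligible or never treated. A definition may sit in the statistical analysis plan, which was not available. The sentence on imputation closes a bullet about summary statistics, and not imputing a value is different from deleting a patient from a denominator. Section 8.3.2 censors some patients who stop for reasons other than progression, even when progression is then found, but that rule is written for time-to-event PFS and not for the one-year count.

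There are also safeguards. Any death is an event. Patients who stop for reasons other than progression have three-monthly visits with CT for up to 12 months or until progression (Sections 3.2 and 6.3). Section 4.3 asks sites to document the outcome, and Appendix 4 asks them to keep seeking objective progression after treatment stops. Many of these failures will be captured.

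All of this stands, and it makes the bias conditional. It does not supply the missing rule. The group on which the decision rests is undefined, the bar depends on its size, and patients whose stopping reason is disease progression have no imaging listed at their only later visit. By contrast, Section 7.2.1 gives the second-course response an explicit denominator: all patients who received that course.

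**Conclusion.** The point holds as a gap in the decision rule, not as a demonstrated bias. If treated patients without a one-year status are excluded, and more than about 85% of them are failures, the one-year rate is biased upward by at most about 1.7 points at p0 with 10% excluded. The false-success risk then rises by about 5 points from the rule's own 5.3% at a bar of 13, or about 3 points from 2.6% at 14. If only half of the six are certain failures, the rise is about 2 points or 1 point. Setting 10.6% against 3.3% and attributing the whole difference to exclusion would be wrong, because 13 of 54 already runs at 5.3%.

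The result does not depend on informative loss alone. If everyone is evaluable and the bar stays at 13, exact alpha is 10.6%. None of these counts meets the stated 3.3% at a bar of 13, apart from unknown-status groups that fail clearly less often than the cohort, which is not the situation the protocol's own stopping reasons suggest. The assumptions are 60 treated per cohort, a true rate of exactly 15%, and the protocol's 10% as the share of unknown status.

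**What to change.** State in Section 8.1, or in the analysis plan before one-year results are tabulated:
- The primary population in each tested cohort is all patients who started treatment.
- A patient without a documented progression-free status at one year counts as not progression-free.
- The cut-off is the smallest one whose exact binomial alpha is within 0.033 for the actual number treated; for 60 it is 15 (alpha 2.9%, power 90.6% if 32% holds among all treated).
- The evaluable-only rate, with evaluable defined, and the Kaplan-Meier one-year estimate are sensitivity analyses.

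This costs wording and a recomputed cut-off, and no further patients, which matters because all cohorts are closed to inclusion. The downside is power. If losses are unrelated to outcome, 15 of 60 has about 85% power with 5% lost and 78% with 10% lost. The fair comparator is 86.6% for 14 of 54, the alpha-valid rule on the planned evaluable number, rather than the 92.1% of 13 of 54, which does not hold its alpha. The stated 90% power should be restated accordingly.

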2 STUDY OBJECTIVES

2.1 Primary objective

To determine the 1 year progression-free survival rate (based on RECIST v1.1.) under combined SABR and anti-PDL1 atezolizumab therapy:

- in patients with metastatic colorectal cancer (cohort closed to inclusions);
- in patients with metastatic non-small lung cancer (cohort closed to inclusions);
- in patients with metastatic renal cell carcinoma (cohort closed to inclusions);
- in patients with metastatic sarcoma (cohort closed to inclusions).

Each cohort will be analysed separately.

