9.4 Data Safety Monitoring Board (DSMB)

A DSMB will be organised under the supervision of the coordinating investigator and composed of people well trained in the field of clinical research in oncology not directly involved into the current trial.

The DSMB will meet after the first 15 patients are enrolled and then when one third, half and then two third of the inclusions are met.

The role of the DSMB is to advise on the safety of the trial and to give advice regarding the continuation of the study.

In the meantime, up to the first 15 patients are enrolled, meeting or teleconferences will be organised after the first 5 patients and then after the first 10 patients are enrolled between the coordinating investigator and investigators from sites where patients were enrolled to review safety data. End of meeting reports will be sent to DSMB members within 2 working days after meeting or teleconferences. If deemed necessary by a DSMB member or the coordinating investigator or the sponsor, a DSMB will be organized before the first 15 patients are enrolled.

In case of disagreement between DSMB and investigators, Competent Autorities will be informed and will receive meeting reports.

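### The synopsis gives two total sample sizes, 138 and 187; only 187 matches section 8.1, and 138 cannot supply the 162 evaluable patients that the three primary tests need

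*Protocol*

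**What the plan says.** Section 8.1 builds the total from the per-cohort design. For each tested cohort it says "we need to enroll 54 evaluable patients", with null and target one-year progression-free rates of 15% and 32%, a one-sided alpha of 0.033 (a global 0.1 divided over three tests) and 90% power. A cohort succeeds if at least 13 patients are alive and progression-free at one year. Allowing for 10% non-evaluable patients and 7 renal patients who are not tested, it concludes that "the total number of patients will be 187 = 3 * 60 + 7 to achieve 162 evaluable patients total".

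The synopsis has two rows on the same subject. Its sample-size row repeats the design and says "the overall expected sample size will then be 187 evaluable patient", with 60 each for lung, colorectal and sarcoma and 7 for renal. Its row for the number of patients gives a total of 138.

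All four cohorts are closed in this version; section 2.1, for example, reads "in patients with metastatic sarcoma (cohort closed to inclusions". Section 8.1 nevertheless still describes the three tested cohorts as open.

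For the response endpoint after a second SABR course, section 8.1 says that the threshold will be recomputed for the number of patients actually re-irradiated. It says nothing of the kind for the primary cut-off of 13.

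**The concern.** One version of the protocol carries two totals that differ by 49 patients (49/187 = 26%), both in current text. The synopsis therefore disagrees with itself as well as with section 8.1. It also uses the word evaluable for a figure that section 8.1 treats as enrolled.

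The total matters because the primary rule is an absolute count. Thirteen successes mean one thing out of 54 and another out of 40. If a cohort closed with fewer than 54 evaluable patients, a fixed count of 13 could declare failure because the cohort was small, and that failure would be read against a stated power of 90%. The reader cannot tell from the protocol whether this has happened.

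**Working it through.** **Inputs.** From section 8.1: p0 = 0.15, p1 = 0.32, alpha = 0.033 one-sided, power 0.90, 54 evaluable per cohort, cut-off 13, 10% non-evaluable, 7 renal patients. From the synopsis: totals of 138 and 187.

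**Reproducing the plan's figures.** The one-stage normal approximation is

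n = [(z(1−α)·√(p0·q0) + z(0.90)·√(p1·q1)) / (p1 − p0)]²

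With z = 1.838 and 1.282 this gives n = 54.4, so 54 reproduces to within a patient. Then 54/0.9 = 60, 3 × 60 + 7 = 187 and 3 × 54 = 162. The 187 enrolled and 162 evaluable in section 8.1 are consistent with each other. The synopsis's 187 evaluable is not consistent with them.

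**Can 138 be reconciled?** With the renal patients included, 138 − 7 = 131 and 162 − 131 = 31 short, with every patient evaluable. With the renal patients excluded, 162 − 138 = 24 short. No split helps: 60 + 60 + 11 + 7 = 138 fills two cohorts and leaves the third with 11. At least one cohort falls below 54. This step assumes nothing about what 138 represents.

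**What it would mean if 138 were accrual.** This part is conditional. It assumes that 138 is the number enrolled, that it includes the 7 renal patients, and that the rest are split evenly: 131/3 = 43.7, rounded to 44 per cohort, or 43.7 × 0.9 = 39.3, rounded to 39, after the stated 10% loss. Exact binomial figures are P(X ≥ r | n, 0.15) for type I error and P(X ≥ r | n, 0.32) for power.

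| Evaluable n | Cut-off r | Exact type I error | Exact power at 32% |
|---|---|---|---|
| 54 | 13 (as stated) | 0.053 | 92% |
| 54 | 14 | 0.026 | 87% |
| 44 | 13 (as stated) | 0.010 | 69% |
| 44 | 12 | 0.026 | 80% |
| 39 | 13 (as stated) | 0.003 | 49% |
| 39 | 11 | 0.025 | 75% |

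The cut-offs 14, 12 and 11 are the smallest that keep exact type I error within 0.033 at each n. These rows are the like-for-like comparison: 87% at 54, 80% at 44 and 75% at 39, a loss of 7 to 12 points. The larger falls, to 69% and 49%, arise only if the count of 13 is kept at the smaller n.

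The stated pair of 13 out of 54 has an exact type I error of 0.053, above 0.033. It should not serve as the benchmark that a smaller cohort fails to meet.

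**The case against.** The best defence is that 187 is plainly the design figure. It appears twice and follows from the stated inputs, while 138 appears once, in an administrative row, and nothing in section 8 uses it. It may be a leftover total. On that view 54 patients, 90% power and a cut-off of 13 remain the planned design, and the fault is one wrong cell. This stands as far as it goes: the contradiction is certain, the loss of power is not.

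Two stronger readings are tempting. One is that the trial enrolled 138 patients and is underpowered. The cohorts are marked as closed, but no accrual number is given, so the protocol does not support that reading. The other is that the safety board's review points move with the total, since section 9.4 sets reviews "then when one third, half and then two third of the inclusions are met". That section gives no patient number, and with inclusion closed those review points can no longer shift, so no consequence follows there.

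It is also fair to say that replacing the planned 187 by accrual would erase the prospective design, and that cut-offs for a realised sample size are often left to the analysis plan, which is not shown. The first point is accepted in the fix. The second has less force here. The protocol itself fixes the primary cut-off as a bare count and provides for recomputation of the other threshold only.

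**Conclusion.** The point holds as an internal contradiction: 138 against 187 within the synopsis and between the synopsis and section 8.1, plus a mislabelled 187. The gap is 49 patients, and 138 falls 31 short of the required 162 evaluable (24 short if the renal patients are not counted in it). None of this needs an assumption about accrual.

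The effect on power is conditional. If 138 is actual accrual, the stated 90% power and the count of 13 do not apply to every cohort. With an even split, power at 32% is 69% (n=44) or 49% (n=39) under the fixed count. With exact alpha held at 0.033 it is 80% or 75%, against 87% at n=54. An uneven split would spare up to two cohorts and hurt the third more. A reader should not infer that the trial has been shown to be underpowered, or that 13 out of 54 meets the stated alpha.

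**What to change.** 1. In the synopsis and section 8.1, keep 187 enrolled and 162 evaluable in the tested cohorts, labelled as the planned size, and correct the word evaluable where the synopsis attaches it to 187.
2. Either correct 138, or label it as actual enrolment and give enrolled and evaluable numbers for each cohort.
3. Correct the description in section 8.1 of three open cohorts, since all are closed.
4. Before the primary analysis, state that the primary cut-off is recomputed by exact binomial at alpha 0.033 for each cohort's actual evaluable number, in line with the recomputation that section 8.1 already provides for the second-SABR endpoint, and restate the power that results.

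The cost is wording in the synopsis and section 8.1, carried into the analysis plan. The restated power may be lower than 90%: even at 54 evaluable patients, holding exact alpha at 0.033 gives a cut-off of 14 and 87%. No further enrolment is proposed.
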